3.1.2 Dose Limiting Toxicities / Treatment Limiting Toxicities

A DLT is defined by the occurrence of any of the following toxicities according to CTCAE v5.0 during treatment Cycle 1 and that are considered by the investigator to be possibly, probably, or definitely related to CyPep-1:

3. Any Grade ≥ 3 AEs of any etiology, except:
 - o Nausea, vomiting, or diarrhea will be considered a DLT only if it persists at Grade ≥ 3 for > 3 days despite adequate supportive care measures. At the investigator's discretion, subjects who experience nausea, vomiting, or diarrhea after receiving CyPep-1 may receive antiemetic or anti-diarrheal medication prior to subsequent doses of CyPep-1.
 - o Isolated laboratory abnormalities Grade ≥ 3 (not present at baseline) that resolve to Grade ≤ 1 in ≤ 7 days without clinical sequelae or need for therapeutic intervention.
 - o Fatigue Grade ≥ 3 for ≤ 7 days.
 - o For Phase I, Arms A and C:
 - Alanine amino transferase (ALAT) or Aspartate amino transferase (ASAT) toxicities:
 - ALAT or ASAT $> 5 \times$ upper limit of normal (ULN) ($> 7.5 \times$ ULN for subjects with liver metastases), unless greater than 14 days.
 - ALAT or ASAT $> 5 \times$ ULN ($> 7.5 \times$ ULN for subjects with liver metastases) accompanied by an elevation in total bilirubin of $> 2.5 \times$ ULN (not explained by obstruction), regardless of duration, will be considered a DLT.
4. Any other toxicity occurring at any time during the trial that in the view of the participating investigators and the medical monitor represents a clinically significant hazard to the subject.

All TLTs will be graded using NCI CTCAE v5.0 based on the investigator assessment. The TLT window of observation will be during Cycle 1.

The occurrence of any of the following toxicities during Cycle 1 will be considered a TLT, if assessed by the investigator to be possibly, probably, or definitely related to trial treatment administration.

1. Grade 4 nonhematologic toxicity (not laboratory).
2. Grade 4 hematologic toxicity lasting ≥ 7 days, except thrombocytopenia:
 - Grade 4 thrombocytopenia of any duration
 - Grade 3 thrombocytopenia associated with clinically significant bleeding

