3. Any non-hematologic AE \geq Grade 3 in severity should be considered a TLT, with the following exceptions: Grade 3 fatigue lasting ≤ 3 days; Grade 3 diarrhea, nausea, or vomiting without use of anti-emetics or anti-diarrheal per standard of care; Grade 3 rash without use of corticosteroids or anti-inflammatory agents per standard of care.
4. Any Grade 3 or Grade 4 non-hematologic laboratory value if:
 - Clinically significant medical intervention is required to treat the participant or
 - The abnormality leads to hospitalization, or
 - The abnormality persists for > 1 week.

- The abnormality results in a Drug-induced Liver Injury (DILI)
- Exceptions: Clinically nonsignificant, treatable, or reversible laboratory abnormalities including liver function tests, uric acid, etc.

5. Febrile neutropenia Grade 3 or Grade 4:

- Grade 3 is defined as ANC <1000/mm³ with a single temperature of >38.3 degrees C (101 degrees F) or a sustained temperature of ≥38 degrees C (100.4 degrees F) for more than 1 hour
- Grade 4 is defined as ANC <1000/mm³ with a single temperature of >38.3 degrees C (101 degrees F) or a sustained temperature of ≥38 degrees C (100.4 degrees F) for more than 1 hour, with life-threatening consequences and urgent intervention indicated.

6. Prolonged delay (>2 weeks) in initiating Cycle 2 due to treatment-related toxicity.

7. Any treatment-related toxicity that causes the participant to discontinue treatment during Cycle 1.

8. Missing >25% of CyPep-1 doses as a result of drug-related AE(s) during the first cycle.

9. Grade 5 toxicity.

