4. SELECTION OF TRIAL POPULATION

4.1 Inclusion Criteria

For Phase I and Phase IIa Arms A and C:

1. Histologically or cytologically confirmed locally advanced (unresectable) or metastatic tumors (solid tumor or lymphoma) with an accessible tumor lesion for intratumoral injection of CyPep-1 malignancy (including lymphomas) that is either:
 - a. Refractory to standard-of-care treatment
 - b. Have a disease for which there is no standard therapy considered appropriate. Metastatic deposits (including cutaneous/subcutaneous lesions and metastatic deposits in lymph nodes) of tumors for which IT injections may be performed are eligible. Pure cutaneous infiltrations (e.g., breast cancer cutaneous carcinomatosis) are ineligible.
2. 1 to 3 non-ulcerated transcutaneously accessible lesion(s) for injection and measurable as defined by iRECIST. All other tumor lesion(s) may be selected for efficacy follow-up, but will not be subjected to treatment with CyPep-1.
3. Presence of tumor lesion(s) (that have not been previously irradiated) suitable for biopsy at screening and at Week 6.

For Arm C:

4. Confirmation of the presence of at least one liver metastasis by imaging.
5. Subjects must have measurable disease which is equal to one or more metastatic liver lesions that can be accurately and serially measured; that are greater than 1 cm dimension and for which the longest diameter is greater or equal to 1 cm as measured by CT (computed tomography) scan or magnetic resonance imaging (MRI). The metastatic liver lesion(s) must not be in an area that received prior localized therapies.
6. Metastatic liver lesion(s) for injection with >50% radiological visible necrosis must be avoided and the lesion must be located where any tumor swelling will not lead to gall bladder tract obstruction or lead to bleeding risk.

For Arm D:

7. Histologically or cytologically confirmed diagnosis of advanced (unresectable Stage III) or metastatic (Stage IV: M1a and/or M1b) melanoma considered incurable by the standard of care. For metastatic melanoma, only cutaneous, subcutaneous, lymph node, or lung metastases are allowed.
8. Previously exposed to ICI(s) and be categorized following the SITC Immunotherapy Resistance Taskforce ([Kluger 2020](#)) meeting one of the following:
 - a. Have primary resistance: PD-(L)-1 inhibitor exposure ≥6 weeks and have the best response as one of the following:
 - i. PD,
 - ii. SD for <6 months.

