17. All subjects of childbearing potential (defined as < 2 years after last menstruation or not surgically sterile) must have a negative highly sensitive pregnancy test at screening (urine/serum) and agree to use highly effective method for contraception according to the EU Clinical Trial Facilitation Group guidance from time of signing the informed consent form (ICF) until at least 120 days after the last administration of CyPep-1. The partners of subjects with childbearing potential must also apply contraceptive methods and are recommended not to donate sperm.
18. A male participant must agree to use contraception and refrain from sperm donation during the treatment period and for at least 120 days after the last dose of trial medication.
19. Adequate bone marrow, liver, and renal function:
 - a. Platelet count $\geq 100 \times 10^9/L$
 - b. Hemoglobin $\geq 6.0 \text{ mmol/L}$ or 9.67 g/dL
 - c. Absolute Neutrophil Count (ANC) $\geq 1.5 \times 10^9/L$
 - d. Total bilirubin $\leq 1.5 \times \text{ULN}$, except for subjects with familial bilirubinemia (Gilbert's disease)
 - e. Serum ASAT and ALAT $\leq 2.5 \times \text{ULN}$ ($\leq 5 \times \text{ULN}$ in case of liver metastases)
 - f. Creatinine clearance $\geq 30 \text{ mL/min}$ (Glomerular Filtration Rate [GFR] to be calculated by CKD-EPI formula)

For Phase IIa Arm B:

Participants are eligible to be included in Arm B of the trial only if all of the following criteria apply:

Type of Participant and Disease Characteristics

20. The participant provides written informed consent for the trial.
21. Be ≥ 18 years of age on day of signing informed consent.

22. Participant with histologically or cytologically confirmed diagnosis of advanced (unresectable Stage III) or metastatic (Stage IV) solid tumor malignancy (including lymphomas) that is refractory to standard-of-care treatment or for which there is no standard therapy considered appropriate. Metastatic deposits (including cutaneous/subcutaneous lesions and metastatic deposits in lymph nodes) of tumors for which IT injections may be performed are eligible. Pure cutaneous infiltrations (e.g., breast cancer cutaneous carcinomatosis) are ineligible.

23. Subjects must have progressed on treatment with an anti-PD1/L1 monoclonal antibody (mAb) administered either as monotherapy, or in combination with other checkpoint inhibitors or other therapies. Treatment progression is defined by meeting all of the following criteria:

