4.3.2 Replacement of Subjects

In Phase I, replacement for subjects who drop out for any reason, except DLTs, will only occur before the DLT observation period is completed and is allowed if a subject does not receive all three CyPep-1 administrations, unless due to CyPep-1-related toxicity.

No subject replacement will occur for subjects who withdraw later or for subjects who are part of the Phase IIa expansion monotherapy Arms A and D.

For Arm B, replacement of the first 3 subjects is allowed if a subject drops out for any reason, and does not receive all three CyPep-1 injections of the first cycle, unless due to CyPep-1 and/or pembrolizumab related toxicity (TLT) during the TLT observation period. In case of pembrolizumab-related toxicity, treatment with CyPep-1 will be delayed and planned after a review by the investigator and medical monitor. If CyPep-1 treatment is delayed > 7 days, that dose will be omitted. If the delay is > 7 days during the TLT observation period, the subject will be replaced. No subject replacement will occur for subjects who discontinue later.

For Arm C, replacement for subjects who drop out for any reason, except DLTs, before the DLT observation period is completed is allowed when a subject did not receive all three CyPep-1 administrations. No subject replacement will occur for subjects who discontinue later.

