5.3.6.1 Dose Modifications and Management of CyPep-1 associated AEs

CyPep-1 associated hematological and non-hematological adverse effects according to CTCAE v5.0 toxicity grade may occur. Toxicity management and dose modifications are listed below:

Dose adjustments according to CTCAE toxicity grade for drug-related AEs

Occurrence	Grade 1	Grade 2	Grade 3	Grade 4
First appearance	No action with study drug.	No action with study drug.	Interrupt treatment until resolved to Grade 0-1 (or according to inclusion criteria). If interruption is < 14 days, restart at next lower dose level. If interruption is ≥14 days, check with Medical Monitor.	Discontinue study drug.

Second appearance		Discontinue study drug.	
-------------------	--	-------------------------	--

5.3.6.2 Dose modification and toxicity management for immune-related AEs associated with pembrolizumab

AEs associated with pembrolizumab exposure may represent an immunologic etiology. These immune-related AEs (irAEs) may occur shortly after the first dose or several months after the last dose of pembrolizumab treatment and may affect more than one body system simultaneously. Therefore, early recognition and initiation of treatment is critical to reduce complications. Based on existing clinical study data, most irAEs were reversible and could be managed with interruptions of pembrolizumab, administration of corticosteroids and/or other supportive care. For suspected irAEs, ensure adequate evaluation to confirm etiology or exclude other causes. Additional procedures or tests such as bronchoscopy, endoscopy, skin biopsy may be included as part of the evaluation. Based on the severity of irAEs, withhold or permanently discontinue pembrolizumab and administer corticosteroids. Dose modification and toxicity management guidelines for irAEs associated with pembrolizumab are provided in Table 3.

Table 3. Dose Modification and Toxicity Management Guidelines for Immune-related AEs Associated with Pembrolizumab

General instructions:				
irAEs	Toxicity grade (CTCAE V5.0)	Action with pembrolizumab	Corticosteroid and/or other therapies	Monitoring and follow-up

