Hyperthyroidism	Grade 2	Continue	Treat with nonselective beta-blockers (eg, propranolol) or thionamides as appropriate	Monitor for signs and symptoms of thyroid disorders
	Grade 3 or 4	Withhold or permanently discontinue ^d		
Hypothyroidism	Grade 2, 3 or 4	Continue	Initiate thyroid replacement hormones (eg, levothyroxine or	Monitor for signs and symptoms of thyroid disorders

			liothyronine) per standard of care	
Nephritis: grading according to increased creatinine or acute kidney injury	Grade 2	Withhold	Administer corticosteroids (prednisone 1 to 2 mg/kg or equivalent) followed by taper	Monitor changes of renal function
	Grade 3 or 4	Permanently discontinue		
Neurological Toxicities	Grade 2	Withhold	Based on severity of AE administer corticosteroids	Ensure adequate evaluation to confirm etiology and/or exclude other causes
	Grade 3 or 4	Permanently discontinue		
Myocarditis	Grade 2, 3 or 4	Permanently discontinue	Based on severity of AE administer corticosteroids	Ensure adequate evaluation to confirm etiology and/or exclude other causes
Exfoliative Dermatologic Conditions	Suspected SJS, TEN, or DRESS	Withhold	Based on severity of AE administer corticosteroids	Ensure adequate evaluation to confirm etiology or exclude other causes
	Confirmed SJS, TEN, or DRESS	Permanently discontinue		
All Other irAEs	Persistent Grade 2	Withhold	Based on severity of AE administer corticosteroids	Ensure adequate evaluation to confirm etiology or exclude other causes
	Grade 3	Withhold or discontinue based on the event ^e		
	Recurrent Grade 3 or Grade 4	Permanently discontinue		

AE(s)=adverse event(s); ALT= alanine aminotransferase; AST=aspartate aminotransferase; CTCAE=Common Terminology Criteria for Adverse Events; DRESS=Drug Rash with Eosinophilia and Systemic Symptom; GI=gastrointestinal; IO=immuno-oncology; ir=immune related; IV=intravenous; SJS=Stevens-Johnson Syndrome; T1DM=type 1 diabetes mellitus; TEN=Toxic Epidermal Necrolysis; ULN=upper limit of normal.

Note: Non-irAE will be managed as appropriate, following clinical practice recommendations.

^a AST/ALT: >3.0 to 5.0 x ULN if baseline normal; >3.0 to 5.0 x baseline, if baseline abnormal; bilirubin:>1.5 to 3.0 x ULN if baseline normal; >1.5 to 3.0 x baseline if baseline abnormal

^b AST/ALT: >5.0 to 20.0 x ULN, if baseline normal; >5.0 to 20.0 x baseline, if baseline abnormal; bilirubin:>3.0 to 10.0 x ULN if baseline normal; >3.0 to 10.0 x baseline if baseline abnormal

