^c AST/ALT: >20.0 x ULN, if baseline normal; >20.0 x baseline, if baseline abnormal; bilirubin: >10.0 x ULN if baseline normal; >10.0 x baseline if baseline abnormal

^d The decision to withhold or permanently discontinue pembrolizumab is at the discretion of the investigator or treating physician. If control achieved or ≤ Grade 2, pembrolizumab may be resumed.

^e Events that require discontinuation include but are not limited to: encephalitis and other clinically important irAEs (eg. vasculitis and sclerosing cholangitis).

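### The transaminase exception in the DLT definition has no grade ceiling, so an isolated related Grade 4 ALAT/ASAT rise of up to 14 days is not a DLT under the Grade 3-or-higher rule

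*Protocol*

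**What the plan says.** **DLT definition (Protocol Section 3.1.2; same text in the Synopsis).** A related Grade 3 or higher event in Cycle 1 is a DLT, subject to a list of exceptions. For Phase I and Arms A and C the list includes ALAT or ASAT above 5x ULN, with 7.5x in place of 5x when the liver is involved: "ULN for subjects with liver metastases), unless greater than 14 days". A companion line makes the elevation a DLT at any duration if total bilirubin exceeds 2.5x ULN without obstruction. A general laboratory exception covers isolated Grade 3 or higher values that return to Grade 1 or lower within 7 days without sequelae or treatment. A separate item lets the investigators and the medical monitor call any other toxicity a DLT if they judge it a significant hazard.

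**Population (Section 4.1).** Arm C requires "Confirmation of the presence of at least one liver metastasis by imaging". Criterion 19e admits ASAT/ALAT up to 2.5x ULN, or up to 5x ULN "in case of liver metastases".

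**Grades (footnotes to Table 3).** Grade 3 is ">5.0 to 20.0 x ULN, if baseline normal; >5.0 to 20.0 x baseline, if baseline abnormal". Grade 4 is ">20.0 x ULN, if baseline normal; >20.0 x baseline, if baseline abnormal".

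**Action (Section 5.3.6.1).** For a drug-related Grade 4 event at first appearance the table says "Discontinue study drug". The opening of Section 5.3.6 and the Synopsis dose-modification text speak only of delay.

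**Arm B comparison (Section 3.1.2, TLT item 7).** "Any treatment-related toxicity that causes the participant to discontinue treatment during Cycle 1" is a TLT. The DLT list has no such item.

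**Replacement (Section 4.3.2; also the Synopsis and SAP Section 6.1).** "For Arm C, replacement for subjects who drop out for any reason, except DLTs, before the DLT observation period is completed is allowed" when not all three injections were given. The Phase I paragraph of Section 4.3.2 also rules out replacement when the cause is CyPep-1-related toxicity. The Arm C sentence does not.

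**The concern.** The protocol treats one event in two ways. Its action table regards a related Grade 4 transaminase rise as grounds for ending CyPep-1. Its DLT rule leaves the same event out of the toxicity count if it stays within 14 days and bilirubin is not raised.

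DLTs are part of the primary endpoint. In Arm C they are the count on which a 3+3 design moves from 2 to 5 mg/mL given directly into liver metastases. Liver enzymes are the laboratory signal one would most want that count to register. A toxicity severe enough to stop dosing should enter it by rule.

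**Working it through.** The plan states no DLT rate or operating characteristic for the 3+3 design, so there is no figure to reproduce. The check traces one event through the rules.

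**1. Grade boundaries.** Let b be the baseline in multiples of ULN and B = max(1, b). From the Table 3 footnotes, Grade 3 starts above 5B and Grade 4 above 20B (x ULN).

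| Baseline (x ULN) | Grade 3 above | Grade 4 above |
|---|---|---|
| 1 or less | 5 | 20 |
| 1.5 | 7.5 | 30 |
| 2.5 (entry limit, no liver metastases) | 12.5 | 50 |
| 5 (entry limit, liver metastases) | 25 | 100 |

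The lowest Grade 4 value is just above 20x ULN. That is 20/7.5 = 2.7 times the exception threshold with liver metastases and 20/5 = 4 times the threshold without. Every Grade 4 transaminase value therefore falls inside the exception.

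**2. Two readings of the bullet.** It can mean that elevations above the threshold are exempt until they pass 14 days. It can also mean that they are DLTs only if they pass 14 days. On both, a Grade 4 rise of up to 14 days with no qualifying bilirubin rise is not a DLT under the Grade 3-or-higher rule.

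**3. Traced case.** Take an Arm C subject at 2 mg/mL with normal baseline, related ALAT of 21x ULN, normal bilirubin, and ALAT back below 7.5x ULN by day 14.
- Grade: 21 > 20, so Grade 4.
- DLT rule: 21 > 7.5 and duration no more than 14 days, so excepted.
- Bilirubin rule: not met.
- Action table: discontinue CyPep-1.
- Arm B for comparison: the same stop in Cycle 1 would be a TLT under item 7.

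**4. Effect on the count.** With no other DLT, the cohort reads 0/3 as written and moves to the next dose level. If the event counted, it would read 1/3 and need three more subjects.

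**5. Scale, on assumed rates only.** A dose level passes with 0/3, or with 1/3 followed by 0/3, so P(pass) = (1-p)^3 + 3p(1-p)^5. Let d be the rate of events already counted and x the rate of excepted Grade 4 rises. Assume no replacement and no use of the hazard item. As written p = d; with the fix p = d + x.

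| d | x | As written | With fix |
|---|---|---|---|
| 0 | 0.10 | 1.000 | 0.906 |
| 0 | 0.20 | 1.000 | 0.709 |
| 0.10 | 0.10 | 0.906 | 0.709 |
| 0.10 | 0.20 | 0.906 | 0.494 |

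Neither d nor x is in the documents. The table shows only how strongly the count depends on the definition if such events occur.

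**The case against.** **Tolerance of reversible enzyme rises is a consistent choice.** The 7-day laboratory exception has no height limit. The Arm B list excludes laboratory values from its Grade 4 item and exempts reversible liver-function changes. This stands as a reason to keep a 14-day tolerance at Grade 3. It does not explain why an event that ends dosing is a TLT in Arm B and not a DLT in Arm C.

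**The definition already has a route.** The hazard item is part of the DLT definition, and the committee reviews the safety data before cohort 5 opens. A reader might infer that the event cannot be called a DLT; the documents do not support that. Both routes rest on judgement, however, and the committee is made up of investigators, the medical monitor and sponsor representatives.

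**Stopping is not stated consistently.** Section 5.3.6 and the Synopsis mention only delay. The Section 5.3.6.1 table is the more specific instruction and should prevail, but the conflict is real and needs resolving.

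**Replacement.** A reader might infer that the subject could be replaced and the event erased. The text does not settle this. Section 4.3.1 applies the term trial dropouts to withdrawal of consent, non-compliance and loss to follow-up, and says subjects stopped for safety are not necessarily withdrawn. Section 3.1 and the Synopsis tie Arm C to Phase I procedures. Replacement is also optional, and it does not itself change the DLT count.

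**Reporting.** A reader might infer that the event disappears from the results. It would not. SAP Section 11.1.3 tabulates Grade 3 or higher events and related events leading to CyPep-1 discontinuation, and Section 11.4 plans hepatotoxicity shift tables by liver metastasis. These come after the dose decision.

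**Conclusion.** The point holds in a limited form. The transaminase exception has no grade ceiling, and an isolated related Grade 4 rise of up to 14 days is outside the Grade 3-or-higher DLT rule on either reading. The gap covers Phase I and Arms A and C. Its practical weight is in Arm C, where one uncounted event is the difference between 0/3 and 1/3. The Arm C replacement wording is a secondary inconsistency.

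This assumes that the Table 3 boundaries, given there as CTCAE v5.0 grades for pembrolizumab, also apply to DLT grading, and that the Section 5.3.6.1 table governs action at Grade 4. The DEC analyses are in a Cohort Management Plan (SAP Section 7.3) that is not among the documents and may add detail.

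Two stronger readings go too far. One is that the rule generally counts smaller rises and exempts larger ones. That needs the first reading of the bullet, a baseline below 1.5x ULN and a duration of 8 to 14 days: at a normal baseline, 6x ULN for 10 days would count and 8x would not. The other is that unsafe escalation is likely. No event rate is given, and Section 5.3.4 reports no DLTs, SAEs or discontinuations for AEs at 5 mg/mL in Phase I, although that summary does not speak to injection into liver lesions.

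The correction should be made, because the inconsistency sits in a primary-endpoint definition and wording resolves it.

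**What to change.** 1. In Section 3.1.2 and the Synopsis, limit the exception to Grade 3 for all subjects it covers, with and without liver metastases. Suggested wording: *ALAT/ASAT Grade 3 elevations lasting no more than 14 days without total bilirubin >2.5x ULN are not DLTs. Any related Grade 4 ALAT/ASAT elevation, or any related toxicity leading to permanent discontinuation of CyPep-1 in Cycle 1, is a DLT; this takes precedence over the 7-day laboratory exception.* Keep the bilirubin rule with its 5x and 7.5x ULN thresholds. Capping only subjects with liver metastases would make the rule stricter for them than for everyone else, against the intent of the higher threshold.
2. Align Section 5.3.6 and the Synopsis dose-modification text with the Section 5.3.6.1 table on Grade 4.
3. Add the Phase I exclusion for CyPep-1-related toxicity to the Arm C replacement sentence in Section 4.3.2, the Synopsis and SAP Section 6.1.
4. Apply the change prospectively to Arm C and leave completed Phase I DLT calls as they are.

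The cost is a protocol amendment with matching SAP text. No new data are collected. The downside is that one extra three-subject expansion may be triggered at a dose level, which the 3+3 rule already allows.

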In case in the first 12 subjects at RP2D, a responder per iRECIST (ORR as CR/PR as best response) or 2 subjects with stable disease (SD with duration >16 weeks from onset) per iRECIST are observed, the number of subjects will be expanded to a total of 24 (CyPep-1 monotherapy; subjects cohort 3 of Phase I and in Phase IIa Arm A).

Phase IIa – combination arm (Arm B):

The safety and tolerability of CyPep-1 in combination with pembrolizumab will be evaluated in a cohort of 15 subjects in total, using a staggered approach. Initially, 3 subjects will receive CyPep-1 at RP2D in combination with pembrolizumab and each subject will be observed for 24 h before the next subject can be administered with CyPep-1. After the first 3 subjects completed the TLT observation period of 6 weeks with no TLTs observed and after reviewing the safety data (including TLTs) by the DEC, the inclusion of all remaining subjects at RP2D of CyPep-1 in combination with pembrolizumab can be initiated. In the absence of any TLTs, the 24-h observation period before start treatment of the next subject is no longer applicable. Should any TLTs be observed in the first 3 subjects at the RP2D of CyPep-1 in combination with pembrolizumab, an additional 3 subjects will be included in this dose group. If ≤1 out of 6 subjects have a TLT, the remainder of the 15 subjects will be treated at the RP2D. In the unlikely case that 2 or more of the 6 subjects experience any TLTs at RP2D of CyPep-1, a recommendation to dose de-escalate and to what dose or to continue the combination part of the trial will be made by the DEC. The same screening is planned, and CyPep-1 will be administered according to the same schedule as in Phase I.

Scheduling of treatment of CyPep-1 and pembrolizumab (Arm B) will be as follows: CyPep-1 will be administered every 2 weeks (Q2W) and pembrolizumab will be administered following a Q6W schedule starting on Day 1, as per standard of care. Radiological assessment to determine occurrence of (un)confirmed PD will be performed Q8W from the start of treatment. Treatment will continue until confirmed PD, unacceptable toxicity or consent withdrawal, loss to follow up, or trial end, whichever occurs first.

Phase IIa – dose expansion liver metastases (Arm C):

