3.3 Duration of Subject Participation

Each subject will undergo up to 4 weeks of screening, followed by a DLT/TLT observation period of 6 weeks (5 weeks of CyPep-1 treatment plus 1 week observation). In absence of DLT/TLTs, treatment continues with Q2W intratumoral injections of CyPep-1. For the combination arm (Arm B), plus Q6W administration of pembrolizumab for up to 24 months (18 cycles). For Arm D, after screening, each subject will undergo QW CyPep-1 treatment until the second iRECIST/itRECIST assessment at week 16, followed by a Q2W dosing scheme. Continuous treatment cycles of CyPep-1 and/or pembrolizumab are planned and should follow the Q2W administration schedule until confirmed PD, unacceptable toxicity, death, or consent withdrawal, loss to follow up, or trial end, whichever occurs first.

Hereafter, there will be efficacy (PFS) follow-up every 8 weeks, or until confirmed PD, death, withdrawal of consent, loss of subject to follow-up, or trial end, whichever occurs first.

- Start of inclusion: Q1 2020
- Planned last subject last follow-up visit: last subject's last visit for follow-up

For both phases and all trial arms, subjects will stay in the trial until end of trial or until confirmed disease progression, unacceptable toxicity, death or discontinuation for any other reason.

Phase IIa Arm B:

The maximum number of cycles of pembrolizumab is 18 with an approximately duration of 2 years. Then pembrolizumab will be stopped. CyPep-1 treatment may continue.

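### Arm B: the 6-week TLT period ends on Day 42, but TLT criterion 6 cannot be met until about Day 58, so the rule that releases the remaining 12 subjects cannot take it into account

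*Protocol*

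**What the plan says.** Protocol 3.1.2 lists nine TLT criteria for the combination arm and puts a time limit on all of them: "The TLT window of observation will be during Cycle 1". Criterion 6 is "Prolonged delay (>2 weeks) in initiating Cycle 2 due to treatment-related toxicity". Two other criteria depend on duration. Criterion 2 requires a Grade 4 hematologic toxicity, other than thrombocytopenia, to last at least 7 days. Under criterion 4, one way for a Grade 3 or 4 non-hematologic laboratory value to count is that "The abnormality persists for > 1 week".

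Protocol 3.3 gives the length of the period: "DLT/TLT observation period of 6 weeks (5 weeks of CyPep-1 treatment plus 1 week observation".

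Protocol 3.1 makes Arm B enrolment depend on it. "After the first 3 subjects completed the TLT observation period of 6 weeks with no TLTs observed", and once the DEC has reviewed the safety data, "the inclusion of all remaining subjects at RP2D of CyPep-1 in combination with pembrolizumab can be initiated". Any TLT in the first 3 leads instead to 3 more subjects, and then "If ≤1 out of 6 subjects have a TLT, the remainder of the 15 subjects will be treated at the RP2D".

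The synopsis and SAP 6.1 repeat the 6-week rule. SAP 11.1.3 tabulates TLTs but does not say how an event that meets its criterion after Day 42 is handled.

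**The concern.** A criterion that turns on how late Cycle 2 starts cannot be judged before Cycle 2 is due. If the period closes first, the text lists a criterion that its own window excludes and that the release decision cannot use.

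TLTs in combination with pembrolizumab are part of a primary endpoint (Protocol 2.2.1). The count in the first 3 subjects decides between two courses: release of the other 12 with the 24-hour spacing between starts dropped, or 3 further subjects and a ≤1-of-6 check. One criterion 6 event still pending among the first 3 would move the decision from the second course to the first.

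Criterion 6 is not redundant. Pembrolizumab is given once in Cycle 1, so a decision to withhold it first shows at the dose due on Day 43. Table 3 in Protocol 5.3.6.2 withholds it for several Grade 2 immune-related events, and Section 5.3.2 delays CyPep-1 when there is pembrolizumab-related toxicity. A Grade 2 event that begins after the Day 29 injection would generally fall outside criteria 1 to 5, which turn mainly on Grades 3 and 4. It would fall outside criterion 7 unless treatment is discontinued in Cycle 1, and outside criterion 8 if all Cycle 1 injections were given.

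**Working it through.** **Inputs**
- TLT observation period: 6 weeks (Protocol 3.1, 3.3).
- Last scheduled Q2W CyPep-1 injection of Cycle 1: Day 29 (Schedule of Assessments, Table 1c).
- Start of a later cycle: 2 weeks after the last CyPep-1 injection (Schedule of Assessments, footnote 25), visit window ±3 days (Table 1d).
- Pembrolizumab: Day 1 of each 6-week cycle (Protocol 5.3.2).
- Criterion 6: delay of more than 14 days.

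**Start of Cycle 2 (the plan's own figure)**
- From the injection schedule: 29 + 14 = Day 43.
- From the pembrolizumab cycle: 1 + 42 = Day 43.
- SAP Appendix 4, Table 10, also places C2 D1 on Day 43, so the figure is reproduced.

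**End of the TLT period:** 6 × 7 = Day 42.

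**First day on which criterion 6 can be met**
- Nominal: 43 + 14 = Day 57 is a delay of exactly 2 weeks, so more than 2 weeks is first reached on Day 58. Gap to Day 42: 58 − 42 = 16 days.
- Due day 3 days earlier: 40 + 15 = Day 55. Gap 13 days.
- Due day 3 days later: 46 + 15 = Day 61. Gap 19 days.

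**State of the first 3 subjects at the earliest release.** Starts need be only 24 hours apart. When the third subject reaches Day 42, the first may be only on Day 44. Criterion 6 may then be open in all three.

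**Duration-based criteria.** SAP 11.1.2 counts AE duration as stop − start + 1.
- Criterion 2, onset Day 36: 42 − 36 + 1 = 7 days, so the 7-day requirement is met inside the period. Onset Day 37: 42 − 37 + 1 = 6 days, so it is not.
- Criterion 4, abnormality first seen on Day 36: 7 days by Day 42, which is not more than 1 week. First seen on Day 35: 42 − 35 + 1 = 8 days, which is.

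**Illustration of the effect on the 0-of-3 rule.** The documents give no TLT rate, so both inputs are assumptions: p is the true TLT rate, and f is the share of TLTs met only through criterion 6 and not yet visible at review. With all TLTs seen, P(0 of 3) = (1 − p)³. With the late ones unseen, it is (1 − p(1 − f))³.

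| p | all seen | f = 10% | f = 25% | f = 50% |
|---|---|---|---|---|
| 10% | 72.9% | 75.4% | 79.1% | 85.7% |
| 20% | 51.2% | 55.1% | 61.4% | 72.9% |
| 33% | 30.1% | 34.7% | 42.6% | 58.2% |

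For example, with p = 20% and f = 25%: (1 − 0.20 × 0.75)³ = 0.85³ = 61.4%.

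**The case against.** The case on the other side has real force.

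- *Release is not automatic on Day 42.* The DEC must first review the safety data, and a toxicity holding back the Day 43 dose would generally already be on record. If Cycle 2 starts on time, criterion 6 is settled about a day after the period closes. This stands and limits the effect. Still, no minimum interval before the review is stated, and the rule refers to TLTs observed, not to toxicity that might become one.
- *Cycle 1 could be read as lasting until Cycle 2 starts.* That would bring criterion 6 inside Cycle 1, but it then conflicts with the 6 weeks named in Protocol 3.1 and 3.3. It moves the inconsistency without removing it.
- *Few events are affected.* Related non-hematologic events of Grade 3 or above are mostly TLTs already under criterion 3. For CyPep-1-related events of Grade 1 or 2, Protocol 5.3.6.1 foresees no action at first appearance. This stands: what remains is mainly lower-grade immune-related events for which pembrolizumab is withheld, and some Grade 3 hematologic toxicity.
- *The Cohort Management Plan may deal with this.* SAP 7.3 places DEC analyses there, and it was not available for this review. It may help in practice, but it does not cure the protocol text.

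A reader might infer that a criterion 6 event is lost altogether, or that the first-3 review is the only point at which a TLT can change conduct. The documents do not support this. Protocol 3.1.1 lets the DEC act in Phase IIa on available safety data, including TLTs, and Section 3.4 provides for a temporary hold on enrolment. A reader might also infer that no duration-based event first seen at the Day 36 visit can be judged in time. As the working shows, a Grade 4 hematologic event with onset on Day 36 can reach 7 days by Day 42.

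**Conclusion.** The inconsistency is real and specific. As written, a listed TLT criterion cannot be met within the period to which TLTs are confined, and the DEC may release 12 of 15 subjects before it can be judged. The gap is 16 days on the nominal schedule and 13 to 19 days with the visit window. The documents also leave open whether a later event enters the 0-of-3 count, the ≤1-of-6 count or the SAP's TLT tables. The last of these matters for reporting even if the release decision has already been taken.

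The scope is limited. It covers toxicities that are TLTs only through criterion 6, in a subject whose Cycle 2 start is still pending at the review. A smaller version applies to a criterion 4 abnormality first seen on Day 36 or later that would count only through its duration, and to a criterion 2 event that starts after Day 36. Such events may be missed in the release decision; they are not lost to the trial.

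The conclusion assumes that Cycle 2 is due on Day 43, as both documents imply, and that the delay is counted from the due date. The probabilities in the working rest on assumed rates and show direction and possible size only.

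**What to change.** Reconcile five things: the 6-week period, the restriction to Cycle 1, criterion 6, the duration-based criteria for late-onset events, and the DEC release rule. The places are Protocol 3.1, 3.1.2 and 3.3, the synopsis, and SAP 6.1. The result should be that every listed TLT criterion is consistent with the decision and the count it feeds. The text should also say how an event that meets its criterion after Day 42 is treated in the 0-of-3 and ≤1-of-6 checks, and SAP 11.1.3 should say how it is treated in the TLT tables. Which clinical rule to adopt is for the sponsor and investigators.

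The cost is a few sentences. Depending on the rule chosen, there may also be a wait of about 2 weeks for all remaining Arm B subjects when Cycle 2 is delayed in one of the first 3 (or first 6).
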